In this pilot study, we will evaluate the feasibility and acceptability of our protocol to explore the functional post-operative trajectory in a developmentally and neurologically impaired pediatric population. We will evaluate consent rate, protocol delivery and outcome completion, and acceptability. We will also describe common elements of the experience of these children and their families, including information from a functional skills questionnaire, parental descriptions of pre-post abilities, and parental descriptions of their own quality of life. The objectives of our research are:

Primary outcomes

Objective 1: To evaluate the feasibility and acceptability of our study protocol for children and families living with SNI.

To evaluate feasibility we will use the following evaluation points:

1. Consent rate: The overall average consent rate of children/month.
2. Protocol delivery: The percent of on/off protocol children.
3. Outcome completion: The percent of children with complete outcome measures.

To evaluate acceptability, we will conduct end-of-study interviews with caregivers to assess outcomes related to the ease and utility of participating in the study, including our methods of data collection.

Secondary outcomes:

Our secondary aim is to explore patterns of recovery in children with SNI during the peri-operative period. We will assess:

Objective 1: Function in children with SNI, including exploring patterns in specific domains of gain/loss.

Objective 2: Quality of life in children with SNI and their families

Objective 3: Profile of inflammatory biomarkers to compare children's inflammation levels peri-operatively.

HYPOTHESIS

We expect to confirm feasibility and acceptability of conducting peri-operative research in this population, with at least 12 children consented in 1 year and >85% protocol delivery and outcome completion. We anticipate to be able to measure PoFD, quality of life for children and caregivers, and inflammatory biomarkers.

METHODOLOGY

Study Design

This study will use an observational, pre-post intervention design to evaluate our methods of documenting the post-operative functional trajectory and quality of life in children with SNI and their families during the peri-operative period. We will explore the functional abilities and quality of life of children with SNI and their parent/caregivers pre- and post- major orthopaedic surgery, and we will undertake measurements of inflammatory biomarkers

Study Population

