Our study population will include 12 children with SNI and their parent/caregiver planning to undergo major orthopaedic surgery at the BC Children's Hospital Orthopaedic Clinics. One parent/caregiver may participate per child participant (the same parent/caregiver throughout the study).

Our study defines children with SNI as those with significant neurological disorders and evidence of developmental delay across all domains of daily function, who rely on assistive devices/technology for daily activities and well-being, such as mobility aids or feeding devices⁸ To accurately assess the functional status of our participants for screening pre-operatively, we will use the Gross Motor Function Classification System (GMFCS)³⁰ and the Communication Function Classification System (CFCS)³¹ during participant screening.

The GMFCS is a valid and reliable five-level standardized tool used to classify children and youth with SNI based on their level of movement ability^{30,32-34}. For this study, we will include children classified at Levels II to V. Children in Level II may have difficulty balancing on uneven terrain, inclines, in crowded or confined areas and may require physical assistance or mobility device for walking over long distances. Children in Level III will walk with hand-held mobility devices and use wheeled mobility when traveling long distances. Children in Level IV have severe limitations in their walking ability, including with assistance, and rely on a wheelchair most of the time. Children in Level V have profound physical impairments that impact their head and trunk postural control; they are unable to sit, stand, or walk independently and voluntarily.

The CFCS is a valid and reliable five-level tool used to classify how individuals communicate with familiar and unfamiliar partners³¹. For our study, we will include children at Levels II to V. Children at level II alternates between being sender and receiver but may converse slower. Children at level III will typically communicate effectively with familiar communication partners, but not with unfamiliar partners. Children at Level IV are inconsistent in their ability to communicate with familiar communication partners. Children at Level V are rarely able to communicate effectively, including with familiar people, and often require alternative communication methods to interact.

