We aim to recruit 5 control participants specifically for our biomarker analysis (ie. we will only collect demographics and blood samples). The inclusion of this control group allows for a direct comparison of the pre-, peri-, and post-operative inflammatory responses between children with SNI vs neurotypical patients undergoing similar procedures. This is essential for discerning whether any observed altered biomarkers levels specific to children with SNI (ie. and not seen in neurotypical patients), or if they reflect a generalized postoperative inflammatory response. This comparison strengthens the interpretation of our biomarker findings by providing a baseline, which will reduce the risk of misattributing inflammation-related findings solely to the presence of SNI rather than the general surgical response. Additionally, the inclusion of controls improves the clinical relevance of our study, as it will help determine whether children with SNI exhibit exaggerated, prolonged, or distinct inflammatory responses compared to their neurotypical counterparts. These insights will be critical for guiding future research and potential interventions aimed at mitigating PoFD in children with SNI.

Inclusion Criteria

- 1) Neurotypically developing children (GMFCS I and CFCS I)
- 2) Undergoing major orthopaedic surgical management of musculoskeletal pathology (spine or hip; major defined as a greater than or equal to 90 minute procedure with skin-to-skin contact) at the BC Children's Hospital
- 3) Between 5 and 18 years of age at the time of their surgical procedure

Exclusion Criteria

- 1) Non-English-speaking parents/caregivers

Participant Screening and Recruitment

Participants for this study will be recruited in-person through the BC Children's Hospital Orthopaedic Clinics, including the Orthopedic Cerebral Palsy Clinic (CP Clinic) and the Spine Clinic. Study participants

will receive \$100 remuneration for their participation in the study, and control participants will receive \$50 remuneration for their participation.

Participant Screening

1) Screening through standard-of-care clinical visits

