To assess feasibility, we will evaluate three primary feasibility outcomes at the time of data analysis. We will calculate consent rate, which is the overall average consent rate of children/month; protocol delivery, which is the percent of on/off protocol children; and outcome completion, the percent of children with complete outcome measures.

To assess acceptability, anytime after the 6-week timepoint, we will conduct semi-structured interviews with families to assess their experience in participating in this study. We will also ask families if there were any domains that were not included in our standardized functional/quality of life questionnaire and questions. Parents may select from pre-identified domains as prompts (including pain, energy, and sleep), and may also provide additional insight through open-ended conversation. Interviews will be recorded, transcribed, and analyzed using thematic analysis.

The follow study procedures correspond to our secondary aims:

Our primary tool for this study to measure our outcomes of function and quality of life will be the Caregivers Priorities and Child Health Index of Life with Disabilities (CPCHILD) Questionnaire³⁵, which has

been proved to be both valid and reliable^{35,36}. The CPCHILD Questionnaire is used to assess the effectiveness of interventions aimed at improving and preserving outcomes for children aged 5-18 years old with severe disabilities, based on caregivers' perspectives. This questionnaire includes 37 items collected from the parent/caregiver measured across six domains: Personal Care/Activities of Daily Living; Positioning, Transferring, and Mobility; Comfort and Emotions; Communication and Social Interaction; Health; Child's Overall Quality of Life; with additional sections for Importance of Items to Child's Quality of Life, Facts about the Child, and Facts about the Caregiver. From responses, standardized scores can be retrieved on a scale of 0 to 100 for each domain, as well as a total score, and we will be examining comparisons at the item-level pre/post-operatively.

Parents/caregivers will also be asked to answer two supplemental questions to provide further insight into 1) other areas of function that were not described by CPCHILD and 2) the quality of life of caregivers.

Blood collection of study participants

To collect information regarding the peri-operative inflammatory profile, we will collect blood samples from study participants at all study time points:

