
With respect to statistical analysis of our control group, our primary analysis will involve a group comparison at each timepoint to assess whether, and to what extent, any biomarkers are altered (increased or decreased) in children with SNI compared to our controls. Given the large biomarker panel (approximately 120 biomarkers), data visualization using volcano plots will be employed. Multiple comparison adjustments will be applied using the false discovery rate (FDR) correction method (Benjamini-Hochberg). Biomarker significance will be determined based on effect size thresholds, specifically log2(fold change), with a significance level set at 5% (Type I error). Additionally, associations between biomarkers and study variables (e.g., age, sex) will be explored using Wilcoxon rank-sum tests.

Outcomes

The following outcomes will be utilized to deem our study feasible and acceptable:

Feasibility:

1. Consent rate: An average consent rate of 2-3 children/month
2. Protocol delivery: The protocol can be implemented with >85% protocol delivery.
3. Outcome completion: >85% of outcomes will be complete and measured as scheduled.

Acceptability:

4. General positive report on participation based on semi-structured interview

Secondary outcomes; we will explore pre- and post-operative data to describe patterns in:

1. Function of the child, as scored on the CPCHILD;
2. Quality of life of caregiver, as described by supplemental question;
3. Inflammatory profile of child

DATA STORAGE

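### The consent-rate criterion for feasibility (2-3 children/month) contradicts the hypothesis (at least 12 children in 1 year, or 1.0/month), and its reporting unit is also inconsistent

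*Protocol*

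**What the plan says.** The protocol gives the consent-rate bar in two places.

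- **HYPOTHESIS.** Feasibility and acceptability are expected to be confirmed "with at least 12 children consented in 1 year and >85% protocol delivery and outcome completion".
- **DATA ANALYSIS, Outcomes.** The list opens with "The following outcomes will be utilized to deem our study feasible and acceptable", and its first feasibility item is "Consent rate: An average consent rate of 2-3 children/month". The next two items, protocol delivery and outcome completion, are each set at >85%.

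The measure itself is defined twice in the same unit: "Consent rate: The overall average consent rate of children/month" under STUDY OBJECTIVES, and "We will calculate consent rate, which is the overall average consent rate of children/month" under Outcome Measures. The opening paragraph of DATA ANALYSIS, however, names consent rate together with the other two feasibility outcomes and says that all three will be described as percentages.

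On who is counted, the primary objective reads "To evaluate the feasibility and acceptability of our study protocol for children and families living with SNI". Study Population states "Our study population will include 12 children with SNI and their parent/caregiver". The control-group section states "We aim to recruit 5 control participants specifically for our biomarker analysis".

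**The concern.** Both statements claim to say what counts as feasible, and they match on protocol delivery and outcome completion. They therefore read as one set of criteria written out twice, with only the consent bar different. If recruitment goes exactly as hypothesised, with 12 children over 12 months, one section calls the study feasible and the other does not.

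The pilot is meant to settle the methods for a planned larger study, so its feasibility verdict should follow from a rule fixed in advance. With two bars on record, the choice between them could be made after accrual is known.

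The unit is a separate and smaller problem. A count per month cannot be described as a percentage, and the protocol defines no denominator for a consent percentage.

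**Working it through.** **Inputs**

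- Hypothesis bar: at least 12 children in 1 year (HYPOTHESIS).
- Decision bar: 2-3 children/month (DATA ANALYSIS, Outcomes).
- Planned sample: 12 children with SNI and 5 controls (Study Population; control-group section; Sample Size Justification).
- Pool: an average of 50 children per year for hip or spine surgery (Sample Size Justification).

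**Step 1: put both bars on one scale**

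Rate per month = children per year / 12.

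- Hypothesis: 12 / 12 = 1.0/month.
- Decision list: 2 × 12 = 24 and 3 × 12 = 36, so 24-36 children/year.
- Ratio: 2 / 1.0 = 2 and 3 / 1.0 = 3.

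The 2-3/month figure cannot be reproduced from 12 children in a year.

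**Step 2: find when the planned 12 would meet the decision bar**

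Months needed = 12 / rate, which gives 12 / 3 = 4 months and 12 / 2 = 6 months.

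| Months to consent 12 children | Average per month | At least 12 in 1 year? | At least 2/month? |
|---|---|---|---|
| 4 | 12/4 = 3.0 | yes | yes |
| 6 | 12/6 = 2.0 | yes | yes |
| 7 | 12/7 = 1.71 | yes | no |
| 9 | 12/9 = 1.33 | yes | no |
| 12 | 12/12 = 1.0 | yes | no |

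The verdicts differ for any completion time after month 6 and up to month 12. That is 12 − 6 = 6 of the 12 months in the only consent period the protocol gives.

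**Step 3: check whether counting controls closes the gap**

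12 + 5 = 17 children. Over a year, 17 / 12 = 1.42/month, still below 2. Seventeen children average at least 2/month only up to 17 / 2 = 8.5 months, which leaves 12 − 8.5 = 3.5 months in which the bars disagree.

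**Step 4: compare with the stated pool**

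- Hypothesis: 12 / 50 = 24% of a year's surgical patients.
- Decision bar sustained for a year: 24 / 50 = 48% to 36 / 50 = 72%.

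The protocol does not say how many of the 50 have SNI, so these percentages show only that the two bars make different demands on the clinic.

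**Step 5: check the unit**

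STUDY OBJECTIVES, Outcome Measures and the Outcomes list all use children per month. Only the opening paragraph of DATA ANALYSIS uses percentages.

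**The case against.** The strongest reply is that the bars are compatible. The hypothesis is an expectation with a floor, the Outcomes list names itself as the decision list, and 12 children consented in 4-6 months would satisfy both. It is true that both can be met together, and the list's stated role gives it the better claim to be the operative rule. But the hypothesis also speaks of confirming feasibility, and nothing in the protocol ranks the two. Recruitment at exactly the hypothesised pace would still fail the list.

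A second reply concerns the count. The consent-rate definitions say children without qualification, and no sentence expressly excludes controls. If all 17 count, the period of disagreement falls from 6 months to 3.5. That is correct, so the 6-month figure depends on counting only children with SNI. The wording of the primary objective, the study population and the controls' stated purpose support that reading, and the gap survives either way.

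A third reply is that a consent percentage could be intended, because the screening section (CST Cerner) says eligible and approached patients will be tracked. Such a percentage could be calculated, but it would be a different measure from the one the protocol defines and sets a bar for.

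Finally, this is a small observational pilot and the repair is editorial. That limits the weight of the point without removing it.

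**Conclusion.** The concern holds. The protocol sets two bars for its first primary feasibility outcome, 1.0/month and 2-3/month, a factor of 2 to 3 apart, and nothing in it reconciles them. For the planned 12 children with SNI, the two give opposite verdicts at any completion time after 6 and up to 12 months. That window assumes that consenting stops at 12 and that controls are not counted; the factor of 2 to 3 needs neither assumption. The percentage wording is a lesser inconsistency in the same outcome. The point should be fixed before analysis. The protocol does not show which bar was intended.

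**What to change.** Reconcile HYPOTHESIS and the Outcomes list on one lower-bound threshold for children with SNI, stated with the period over which it is averaged. The sponsor must choose between two options:

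- the Outcomes list becomes at least 1 child with SNI per month over 12 months; or
- the hypothesis becomes 12 children with SNI consented within about 6 months, that is, at least 2/month.

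State that the 5 biomarker controls are not counted towards the consent rate. Amend the opening paragraph of DATA ANALYSIS so that consent rate is reported in children per month and only protocol delivery and outcome completion as percentages. If a consent percentage is also wanted, add it as a separate measure with its own denominator.

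The cost is an edit to one of the two sections, one corrected sentence and one short added statement. The planned 12 children, the procedures and the data collection do not change. The price is that one of the two published bars is given up, so the choice should be dated and made before the accrual results are analysed.

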The Medical Student Research Assistant with Level 2 Cerner access will filter their search on CST Cerner specifically for the 3 surgeons whose patients we have obtained permission to recruit from: Drs. [name], [name], and [name]. This will result in a list of the operating schedule and pre-operative appointments for each surgeon. The RA will then access the patients' charts for those who have a confirmed surgery date or pre-operative visit to screen for our inclusion criteria to determine if they are eligible to be a study participant or a control. Screened eligible patients will be confirmed with the Orthopaedic team RAs prior to approaching the patient. With this, we will track all patients who would be eligible, as well as patients that we approached, in a password protected Excel Spreadsheet housed under our lab's V Drive. We have attached the spreadsheet under Recruitment documents which includes all data we will be collecting as part of this screening.

Participant Recruitment

1) Recruitment at regular clinic visit:

During the standard-of-care clinical visit of patients who will likely undergo surgery within ~6 months (as identified by the RAs/team of each clinic conducting screening), the patient's clinician will ask the

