After confirming patient's eligibility, the RA may approach the patient and their parent/caregiver regarding study participation during their pre-operative visit. During their pre-operative clinical visit, the patient's clinician will ask the patient's parent/caregiver if they are interested in participating in research and will briefly introduce them to the study. If the patient's parent/caregiver is interested, the RA will approach the patient and their parent/caregiver regarding the details of the study. If the parent/caregiver is interested in participating, the RA will then obtain consent from the participants (the parent/caregiver may provide consent on behalf of their child) either electronically on a tablet as an E-Consent through REDCap or on paper. The RA may then proceed to take baseline and outcome measurements for study participants, and only demographic information for control participants. The patient's parent/caregiver may alternatively request additional time to consider participating; in this case, they will be emailed a REDCap link to the consent form that they can fill out from home electronically. Once they have been consented, they can then receive a link to our relevant questionnaires (to be filled before surgery). The RA will then coordinate with the patient's MOA to ensure that the study visit timeline are timed congruently with clinical post-operative follow-up visits.

3) Recruitment on day of surgery

After confirming the patient's eligibility, if it is not possible to recruit at the pre-operative appointment the RA may approach the patient and their parent/caregiver regarding study participation on the day of their surgery prior to when the surgery begins. If the parent/caregiver and child agrees to participate, the RAs may obtain consent/assent and complete the baseline/outcome measurements at this time. The RA will then monitor CST Cerner to ensure that the clinical post-operative follow-up visits are timed congruently with the study visit timeline.

Recruitment video

At all three recruitment types, we will show our recruitment video to the study participants (children with SNI) to provide them with more information about the study prior to their review/signing of the consent form.

Sample Size Justification

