We aim to recruit 12 study participants and 5 control participants for this pilot study, which will be useful to 1) test the feasibility and acceptability of our methods and tools for later use on a larger scale, and 2) allow us to describe patterns in preliminary data to identify early associations that may guide the methodology of a larger study. A sample size of 12 study participants and 5 control participants is likely feasible, as the Orthopedic Clinic sees an average of 50 children for hip/spine surgery each year.

STUDY PROCEDURES

The study will include a total of six timed assessments (**Figure 1**). This includes three primary study assessments to collect functional survey and biomarker data: 1) at baseline (within three months of surgery), 2) 6 weeks post-operatively, and 3) 6 months post-operatively. Additionally, we will conduct three biomarker-specific collections during the time of surgery immediately prior to the initiation of the procedure, 12-24 hours post-operatively, and 1-2 weeks post-operatively, based on the physiology of the sequence of the innate and adaptive immune response systems. Most study assessments will be timed at standard of care visits at the BC Children's Hospital. Each primary study visit will take approximately 25-30 minutes. Total time of participation will be 1.5 – 2 hours. Measures will be taken congruently with standard clinical care data collection where possible to reduce participation burden. Some participants may be recruited exclusively for functional/quality of life data collection while the team awaits approvals for blood collection and storage, to allow for an increased sample size.

Baseline Data Collection

Study participants who have consented will undergo a total of 3 primary study visits and 6 biomarker collections (**Figure 1**). At Study assessment #1, demographic information for the child (including variables such as age, sex, race/ethnicity, primary diagnosis, GMFCS/CFCS/MACS score) and demographic information of the parent/caregiver (age, sex, relationship to child, employment status, household income, race/ethnicity, distance from home to primary medical facility) will be collected. Outcome measures (see below) will also be collected. Baseline data collection aims to capture the initial status of participants before any surgical intervention, providing a reference point for post-operative comparisons.

Outcome Measures

The follow study procedures correspond to our primary aims:

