Further, our Research Nurse will extract medication, surgery, and anesthetic-specific data (e.g. pain management drugs [anti-inflammatory, steroids, and immune-suppressants], surgery duration, anaesthesia-specific exposure) pre- and post-operatively from participants' electronic medical records for our team to better contextualize PoFD and inflammatory response.

Timeline

Measures will be taken at baseline (within three months of surgery), at the time of operation, 12-24 hours following operation, 1-2 weeks following operation, 6 weeks post-operatively and 6 months post-operatively as per the schedule below. Study visits will be timed congruently with standard clinical care visits or pre-operative/post-operative clinic visits.

[figure not shown]

Figure 1. Study timeline for study participants

DATA ANALYSIS

Data analysis will focus primarily on evaluating the feasibility and acceptability of the study protocol. Baseline descriptive data will be presented as median and interquartile ranges, and categorical data by percentages. Primary feasibility outcomes (consent rate, protocol delivery, and outcome completion rates) will be described as percentages. Acceptability data will be analyzed from semi-structured interviews. Qualitative data from interviews with families will be analyzed using thematic analysis to identify common themes and insights regarding their experiences with the study protocol.

For secondary outcomes related to improvement and/or decline, we will describe patterns in 1) child's function, 2) quality of life of child and caregiver, and 3) inflammatory profile pre- and post-operatively. Given our small sample size, we cannot statistically confirm correlations of PoFD and inflammatory biomarkers, though we may detect patterns in specific markers.

In our analysis (all outcome measures), we hope to stratify our results by sub-category of GMFCS 5, as has been done previously. The sub-categories are presence of a gastrostomy tube, a tracheostomy,

history of seizures, and nonverbal status. Patients with 0 impairments will be classified as GMFCS level 5.0, patients with 1 impairment as level 5.1, patient with 2 impairments as level 5.2, and patients with 3 or more impairments as level 5.3. This stratification will allow us to examine participants' response to surgery based on an indicator of severity of their neurological impairment.

Blood collection

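### The primary consent rate is a monthly count with no denominator, so it measures accrual rather than willingness and does not fit the percentage that the analysis section promises

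*Protocol*

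**What the plan says.** Three places give the outcome in children per month. Study Objectives, under Primary outcomes, has "Consent rate: The overall average consent rate of children/month". Outcome Measures repeats it: "We will calculate consent rate, which is the overall average consent rate of children/month". The Outcomes list at the end of Data Analysis sets the success criterion: "Consent rate: An average consent rate of 2-3 children/month".

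The opening paragraph of Data Analysis uses a different scale: "Primary feasibility outcomes (consent rate, protocol delivery, and outcome completion rates) will be described as percentages". It does not say what the percentage is a percentage of.

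Four other statements bear on the point:

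- Participant Screening, item 3 (CST Cerner), describes a log: "we will track all patients who would be eligible, as well as patients that we approached". No outcome or analysis sentence in the protocol uses these counts.
- Participant Recruitment, items 1 and 2: the clinician first asks whether the family is interested, and only then "the RA will approach the patient and their parent/caregiver regarding the details of the study". Item 3 (day of surgery) describes no such first step.
- Sample Size Justification gives the only volume figure: "the Orthopedic Clinic sees an average of 50 children for hip/spine surgery each year". It supports both the 12 SNI children and the 5 controls, so it is not a count of eligible SNI children.
- Hypothesis expects success "with at least 12 children consented in 1 year and >85% protocol delivery and outcome completion".

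**The concern.** A consent rate normally answers the question: of the families asked, how many agreed? The defined quantity answers another one: how many children joined per month? The second depends on how many eligible operations are scheduled and how many families are reached, as well as on how many agree.

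The difference matters in this pilot. The introduction justifies it by families' earlier traumatic experience of care and by the burden of collecting data that care does not require. Whether families say yes is therefore a central feasibility question, and no other success criterion records refusal. Protocol delivery and outcome completion concern enrolled children. The acceptability interviews reach only families who joined.

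At stake are the reading of a primary criterion and its use in planning. A larger study can scale a consent proportion to its own surgical volume. It cannot do so with a monthly count unless it also knows how many families were asked.

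**Working it through.** **Inputs.** Criterion: 2-3 children/month (Outcomes). Expected recruitment: 12 in 1 year (Hypothesis). Surgical volume: 50 a year (Sample Size Justification). The numbers of SNI families eligible and asked are not in the protocol, so a range is assumed.

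**1. The criterion on a yearly scale.** 2 × 12 = 24 and 3 × 12 = 36 children a year. The hypothesis gives 12/12 = 1.0 per month, or (12 + 5)/12 = 1.42 with controls counted. Both lie below 2. The study could thus meet its hypothesis and miss its criterion. That is a separate inconsistency, but it should be settled in the same edit.

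**2. Share of eligible families that must consent to meet the criterion.** Share = (monthly rate × 12) / eligible per year.

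| Eligible per year (assumed) | For 2/month | For 3/month |
|---|---|---|
| 50 (all surgical patients) | 24/50 = 48% | 36/50 = 72% |
| 40 | 24/40 = 60% | 36/40 = 90% |
| 30 | 24/30 = 80% | 36/30 = 120%, impossible |
| 24 | 24/24 = 100% | 36/24 = 150%, impossible |
| 20 | 24/20 = 120%, impossible | 36/20 = 180%, impossible |

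The same criterion asks for anything from about half of families to more than all of them, depending on a number that the protocol does not give.

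**3. What a monthly count leaves unknown.** Twelve consents in 12 months is 1.0 per month in every row below. The intervals are exact (Clopper-Pearson).

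| Families asked (assumed) | Consent proportion | Exact 95% CI |
|---|---|---|
| 15 | 12/15 = 80% | 52-96% |
| 24 | 12/24 = 50% | 29-71% |
| 50 | 12/50 = 24% | 13-38% |

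Every row misses the 2-3/month criterion. The table shows only that the monthly figure does not identify willingness, not that a misleading pass occurs.

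**4. Why the denominator must include the clinician's question.** Suppose 20 eligible families are asked, 6 decline to the clinician, the research assistant approaches the other 14, and 12 consent (invented figures). Consented over approached by the assistant is 12/14 = 86%. Consented over all asked is 12/20 = 60%. A denominator that starts with the research assistant leaves out the earliest refusals.

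**The case against.** Children per month is a legitimate feasibility measure. The unit is stated openly in all three definitions, so few readers would take it for a proportion. Data Analysis also promises a percentage, and the screening log holds its natural denominators. The statistical analysis plan is not at hand and may tabulate the log. All of this is fair. It means the monthly count should stay, and that one can say only that this protocol states no use for the logged counts. It does not remove the defect: the outcome and its threshold are fixed here per month, a monthly count cannot be a percentage, and the denominator is unnamed.

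A reader might infer that the criterion could be passed while most families refuse. The protocol's figures give little support for that. At 2 per month, fewer than half of families agree only if more than 48 are eligible each year (24/48 = 50%). The whole hip/spine volume is 50, before the eligibility criteria are applied.

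A reader might also infer that consented over eligible is the right replacement. It would count eligible families who were never asked as if they had refused. Families asked is the better denominator for willingness.

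Finally, the log's layout is in an attachment that is not shown. It may already have a field for refusals, so one cannot say that clinician-step refusals will be lost.

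**Conclusion.** The point holds. The primary consent rate and its success criterion are an accrual rate, and the protocol contradicts itself on the scale: children per month in three places, a percentage in a fourth, and a denominator in none. Followed as written, the plan gives a figure that cannot separate willingness from surgical volume.

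The likely harm runs in one direction. The lower bound of 2 per month needs 48% consent from 50 eligible families a year, 80% from 30, and cannot be reached below 24. The criterion can therefore fail although families are willing, and the result does not transfer to a larger study with a different volume.

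These percentages assume a steady flow of eligible families over a year and eligible numbers chosen for illustration. The conclusion that the monthly count does not identify the consent proportion does not depend on those choices. The change should be made, since a primary outcome is affected and the remedy is cheap.

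**What to change.** 1. Keep children per month, but label it recruitment (accrual) rate. Reconcile its 2-3/month target with the 12 children in 1 year of the Hypothesis.
2. Define consent rate as SNI families consented divided by eligible SNI families asked, with an exact 95% confidence interval. Count a family as asked once the clinician or the research assistant has raised the study, and count a decline to the clinician as a refusal. State whether a success threshold applies to this proportion.
3. Report asked/eligible and consented/eligible beside it from the existing log, and keep that log for all three screening routes, not only the Cerner route under which it is described.
4. Align Study Objectives, Outcome Measures, the opening of Data Analysis and the Outcomes list.

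**Cost.** Mainly wording, and possibly one more field in the log. With about 12 consents the interval will be wide (36-81% for 12 of 20), and the proportion may look less favourable than a monthly count.
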